- e Habits include recording of caffeine, alcohol, and tobacco consumption.
- f A posterior anterior chest X-ray will be taken locally at screening unless one has been obtained within 3 months of screening (Visit 1) (provided the X-ray and/or report are available for review). Refer to Section 9.4.7 for more details.
- g Refer to rescreening guidance as appropriate (Section 6.4).
- h Evaluation includes historical events and preexisting conditions.
- i Patients need to be asked about presence of eye symptoms; if eye symptoms are present, then an eye examination is required. Refer to Section 9.4.6 for specific instructions.
- j Refer to Section 7.1.1 for specific IP administration instructions.
- k IP compliance will be assessed by review of the Study Drug Administration Log, return of empty or unused investigational product packaging, and/or direct questioning

- l An X-ray of the SIJ will be performed during the Screening Period (Period 1) unless an X-ray taken prior to screening is available for central reading, is of good quality, and confirms diagnosis of r-axSpA. All X-rays require central reading ONLY, regardless of date taken. Central reading will define eligibility using the mNY criteria. If central reading of a preexisting X-ray is not consistent with r-axSpA by central reading, a new X-ray of the SIJ may be taken during Period 1 and sent in for central reading.
- m A Self-Harm Follow-Up Form is to be completed for each discrete self-harm event identified on the C-SSRS and the Self-Harm Supplement Form.
- n HLA-B27 test will be performed centrally.
- o Approval from the Lilly clinical research physician or clinical research scientist must be obtained before a CRP retest is permitted. If the CRP lab is retested, the most recent value will be used for randomization.
- p If the QuantiFERON®-TB Gold test or T-SPOT® is available, either test may be used instead of the PPD TB test. The QuantiFERON®-TB Gold test may be performed locally or centrally; the T-SPOT® must be performed locally. PPD tests must be read 2-3 days after Visit 1. Refer to Section 9.4.7 for more details.
- q For female patients ≥ 40 and < 60 years of age who have had a cessation of menses for at least 12 months, an FSH test will be performed to confirm non-childbearing potential (FSH ≥ 40 mIU/mL or ≥ 40 IU/L). FSH test will be performed centrally.

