5.5. Justification for Dose

The treatment regimen to be evaluated in this study (ixekizumab 80 mg Q4W with a starting dose of 160 mg administered subcutaneously) was selected based on clinical and PK/pharmacodynamic (PD) data from psoriasis, RA and r-axSpA studies.

Extensive dose-ranging studies were conducted in psoriasis and RA populations, exploring multiple doses of ixekizumab in both indications. The dose-ranging study in RA included 2 different patient populations (bDMARD-naïve and TNF-inadequate responders) (Genovese et al. 2014).

Finally, the efficacy of common treatment regimens of other therapies (most TNF inhibitors and secukinumab) has been demonstrated across various rheumatological conditions (RA, PsA, axSpA) (Simponi® package insert, 2015; 2015 package inserts for Cimzia®, Cosentyx®, Enbrel®, and Humira®; Sanford and McKeage 2015).

Collectively, these current internal (ixekizumab) and external (TNF inhibitors and secukinumab) scientific data support the rationale for studying ixekizumab in patients with r-axSpA with the proposed treatment regimen of ixekizumab 80 mg Q4W with a starting dose of 160 mg.

6. Study Population

The study population will include patients with a prior physician diagnosis of axSpA who fulfill protocol criteria for active r-axSpA (with sacroiliitis defined radiographically according to the modified New York [mNY] criteria, based on central reading, associated with at least 1 SpA feature and [Appendix 5]), who have given written informed consent.

Study investigator(s) will review patient history and screening test results from Visit 1 (all criteria), and Visit 2 as per the Schedule of Activities (Section 2) to determine if the patient meets all inclusion and none of the exclusion criteria to qualify for participation in the study. All screening activities must be completed and reviewed before the patient is randomized. Patients may be rescreened in the circumstances described in Section 6.4.

Prospective approval of protocol deviations to recruitment and enrollment criteria, also known as protocol waivers or exemptions, are not permitted.

In this protocol section, the following definitions apply:

- Screening is defined as Visit 1, up to 42 days prior to baseline randomization.
- Baseline randomization visit is defined as Visit 2 (Week 0).

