7.2. Method of Treatment Assignment

Patients who meet all criteria for enrollment will be randomized to double-blind treatment at Week 0 (Visit 2). Assignment to treatment groups will be determined by a computer-generated random sequence using an interactive web-response system (IWRS). The IWRS will be used to assign double-blind investigational product to each patient. Site personnel will confirm that they have located the correct assigned investigational product package by entering a confirmation number found on the package into the IWRS.

To achieve between-group comparability, the randomization will be stratified by baseline CRP (non-elevated or elevated) and TNF inhibitor experienced or naïve. The study will enroll approximately 60% of patients with baseline CRP elevated (>5.00 mg/L) and approximately 40% of patients with non-elevated baseline CRP. At least 61 bDMARD-naïve patients will be enrolled per arm.

Once a specific stratum is fully enrolled, the sponsor may stop further enrollment of patients fitting the criteria of that stratum.

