9.1.2.12. Laboratory Tests Used for Efficacy Measures and Disease Diagnosis

9.1.2.12.1. High Sensitivity C-Reactive Protein

High sensitivity CRP will be the measure of acute phase reactant. It will be measured with a high sensitivity assay at the central laboratory to help assess the effect of ixekizumab on disease activity. The results will not be shared with the investigative sites after baseline randomization to maintain the study blind.

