6.1.1. General Considerations for Analyses during the Blinded Treatment Dosing Period (Period 2)

Comparisons between ixekizumab regimen 80 mg Q4W and placebo will be performed for all analyses in Period 2.

Period 2 starts at the first injection of study treatment at Week 0 (Visit 2) and ends prior to the first injection of study treatment at Week 16 (Visit 8) or the ETV (between Weeks 0 and 16). If a patient has Visit 8 but does not receive injection at Week 16 (Visit 8), the last recorded time for Visit 8 is used as the end time for Period 2.

Baseline will be defined as the last available value before the first injection for efficacy, health outcome, and safety analyses. In most cases, this will be the measure recorded at Week 0 (Visit 2). For efficacy measures, if the patient does not take any injection, the last available value on or prior to randomization date will be used. Change from baseline will be calculated as the visit value of interest minus the baseline value. For safety analyses using a baseline period, the baseline period is defined as the time from Visit 1 to the date/time of the first injection.

The randomization to treatment groups is stratified by baseline CRP status (nonelevated versus elevated) and TNF inhibitors experience (experienced or naïve) as described in Section 5.2. Unless otherwise specified, the statistical analysis models will adjust for baseline CRP status, and prior TNF inhibitors experience(if applicable).

The primary analysis method for treatment comparisons of categorical efficacy and health outcomes variables at specific time points will be made using a logistic regression analysis with treatment, baseline CRP status, and TNF inhibitors experience (if applicable) in the model. The proportions, odds ratio and 95% confidence intervals (CIs) will be reported; treatment difference and 95% CIs will also be reported. Secondary analysis will be conducted using a Fisher's exact test. In the case when logistic regression model does not produce statistical results due to sparse data, Fisher's exact test will be used.

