6.9.1. Primary Outcome and Methodology

The primary outcome is the proportion of patients achieving ASAS40 at Week 16 (Visit 8) in bDMARD-naïve patients. The primary outcome related to improvement in symptomatic feature of AxSpA are assessed at Week 16 (Visit 8) prior to placebo patients being switched to ixekizumab during Period 3 (Extended Treatment Period).

The primary analysis will be based on the ITT Population in bDMARD-naïve patients for the Blinded Treatment Dosing Period (Period 2) comparing the ixekizumab treatment group and placebo at Week 16 (Visit 8). The primary analysis is a logistic regression analysis with treatment and baseline CRP status in the model (Section 6.1.1).

Table RHCH.6.4 provides the detailed analyses including analysis type, method and imputation, population, time point, and treatment comparisons for primary outcome.

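### Does adjusting for baseline CRP status, rather than an explicitly named screening-CRP stratum, damage the primary analysis?

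*SAP*

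**What the plan says.** **Randomisation.** Protocol Section 7.2 states that "the randomization will be stratified by baseline CRP (non-elevated or elevated) and TNF inhibitor experienced or naïve", with elevated meaning above 5.00 mg/L. In the Schedule of Activities, footnote o is attached to the screening CRP only and adds: "If the CRP lab is retested, the most recent value will be used for randomization". Protocol Section 6 requires that "All screening activities must be completed and reviewed before the patient is randomized". On the assay, Protocol Section 9.1.2.12.1 says: "It will be measured with a high sensitivity assay at the central laboratory to help assess the effect of ixekizumab on disease activity". CRP is drawn again at Visit 2, the day of randomisation and first dose.

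**Analysis.** SAP Section 6.1.1 gives a general rule: "Baseline will be defined as the last available value before the first injection for efficacy, health outcome, and safety analyses". It adds that this is usually the Week 0 measurement. The same section says: "The randomization to treatment groups is stratified by baseline CRP status (nonelevated versus elevated", with TNF inhibitor experience as the other factor. The next sentence provides that, unless otherwise specified, "the statistical analysis models will adjust for baseline CRP status" and for TNF inhibitor experience where applicable. SAP Section 6.2 sets the covariate's cut-off at 5.00 mg/L, the same as for randomisation. For the primary endpoint, SAP Section 6.9.1 says: "The primary analysis is a logistic regression analysis with treatment and baseline CRP status in the model".

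Neither document says whether the covariate is taken from the IWRS record or re-derived from the Week 0 sample. Neither has a rule for patients whose two values fall on opposite sides of the cut-off.

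**The concern.** A sample drawn on the randomisation day and sent to a central laboratory could hardly be reported in time to set the stratum, so the stratum must rest on screening CRP, taken up to 42 days earlier. If the general baseline definition also governs the CRP covariate, the model uses a second, noisier match to the factor on which patients were balanced.

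Three things would then be at stake. Part of the precision gained by stratifying could be lost, and the model would not follow the randomisation exactly. The primary model's only covariate would have two possible sources, which leaves the analyst a choice. In the overall population, a few TNF-experienced patients could appear as non-elevated, a combination that the three-stratum design in Protocol Section 5.4 does not contain.

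**Working it through.** **1. The plan's own figure.** Inputs from SAP Section 5.3: response 44% versus 16%, two-sided Fisher's exact test at 0.05, 90% power. Exact enumeration gives power of 0.899 at 60 per arm and 0.905 at 61 per arm. The stated 61 is reproduced, and nothing here alters it.

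**2. How many patients might cross the cut-off.** The documents give no correlation between the screening and Week 0 values, so 0.7 to 0.9 on the log scale is an assumption. With a bivariate normal distribution and a proportion *q* below the cut-off at each draw, discordance = 2 × (*q* − P(both below)).

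The planned 60/40 split applies to the whole study. Since TNF-experienced patients must have elevated CRP, all 0.40 × 140 = 56 non-elevated patients are naïve. With 122 naïve patients, *q* is 56/122 = 0.459. Both values are shown:

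| Correlation | *q* = 0.40 | of 122 | *q* = 0.459 | of 122 |
|---|---|---|---|---|
| 0.7 | 2 × (0.400 − 0.2776) = 0.245 | 29.9 | 2 × (0.459 − 0.3331) = 0.252 | 30.7 |
| 0.8 | 2 × (0.400 − 0.3009) = 0.198 | 24.2 | 2 × (0.459 − 0.3572) = 0.204 | 24.9 |
| 0.9 | 2 × (0.400 − 0.3305) = 0.139 | 17.0 | 2 × (0.459 − 0.3876) = 0.143 | 17.4 |

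So about 17 to 31 of the 122 naïve patients could be coded differently. The choice of split hardly matters.

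**3. What that does to the primary test.** The primary logistic model (treatment plus CRP status, Wald test) was simulated with 61 per arm and 40,000 runs per scenario. Per arm, 28 patients were non-elevated and 33 elevated at screening, with exact balance. Assumed ranges were 10% to 30% discordance and a CRP odds ratio for response of 1.5 or 3, with either the screening or the Week 0 value driving response. Type I error was examined at common response rates of 16% and 30%.

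| | Randomisation stratum | Week 0 status |
|---|---|---|
| Type I error | 0.043 to 0.053 | 0.042 to 0.050 |
| Power, 44% vs 16% | 0.932 to 0.945 | 0.931 to 0.943 |

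The Monte Carlo standard error is about √(0.05 × 0.95 / 40,000) = 0.001, so the differences in type I error are slight.

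The largest power gaps arise at 30% discordance and an odds ratio of 3. When screening CRP drives response, the stratum gives 0.945 and Week 0 gives 0.937. When Week 0 CRP drives response, the stratum gives 0.933 and Week 0 gives 0.941. Each is a gap of about 0.8 points, in opposite directions. A separate run with 14% to 25% discordance and odds ratios of 2 to 4 gave type I error of 0.043 to 0.053 with either coding, and power differences of at most about 1 point.

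**4. The combination excluded by design.** It cannot occur in the primary analysis, which contains only naïve patients. With at most 140 − 122 = 18 TNF-experienced patients and the 60/40 split, the share of elevated patients falling below the cut-off is (0.245 / 2) / 0.60 = 20% to (0.139 / 2) / 0.60 = 12%, or about 2 to 4 patients. The overall models enter CRP status and TNF experience as separate main effects without an interaction, so these patients do not disturb estimation.

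**The case for a change.** The strongest case for a change is that the literal reading has support. Nothing exempts CRP from the general baseline rule. In SAP Section 6.1.1, the repeated-measures model for CRP itself keeps CRP status and drops the baseline value terms, which fits a status computed from the baseline value. The same 5.00 mg/L cut is used to categorise baseline CRP in the patient characteristics table. No passage says that covariates are taken as randomised. The factor also appears in the categorical repeated-measures, MMRM and ANCOVA models and in the stratified log-rank test. Naming the source would cost one sentence.

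It stands that the source is unnamed, and that naming the IWRS stratum would be harmless. It does not stand that the SAP fixes the covariate as the Week 0 value: stratifier and covariate carry one name in adjacent sentences, and adjusting for the factors just listed as stratifiers is a natural reading. Nor does the question reach every model. The efficacy subgroup models, the safety ANCOVA and the Fisher's exact tests contain no CRP status term. Only patients crossing the cut-off would be affected. A sparse fourth stratum could arise in the stratified log-rank test, but that is a supportive analysis without multiplicity control and is run alongside an unstratified test.

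**Conclusion.** The concern does not call for a change. The documents leave the source of one covariate unstated, and either way of filling the gap gives a valid primary analysis, because both CRP measurements precede treatment. Taking the covariate from the randomisation record is the natural choice. An analyst who used Week 0 status would obtain essentially the same error rate, with power within about 1 point. Neither coding is uniformly better: the advantage follows whichever CRP value predicts response more closely.

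This rests on assumed discordance of 10% to 30% and assumed CRP odds ratios of 1.5 to 4, since the documents give neither figure, and on balance within strata. It also assumes the source is settled before unblinding, as any programming detail of this kind would be. Within those ranges there is no demonstrable gain from amending the SAP, and nothing here bears on inclusion criterion 4 or the sample size.

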10.3. Statistical Analyses

Statistical analysis of this study will be the responsibility of Lilly.

Continuous data will be summarized in terms of the mean, standard deviation, minimum, maximum, median, and number of observations. Categorical data will be summarized as frequency counts and percentages.

Any change to the data analysis methods described in the protocol will require an amendment ONLY if it changes a principal feature of the protocol. Any other change to the data analysis methods described in the protocol, and the justification for making the change, will be described in the clinical study report (CSR). Additional exploratory analyses of the data will be conducted as deemed appropriate.

Complete details of the planned analyses will be documented in the SAP.

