When the MMRM is used, the model will include treatment, baseline CRP status, TNF inhibitor experienced or naïve, baseline value, baseline value-by-visit, visit, and treatment-by-visit interaction as fixed factors. The covariance structure to model the within-patient errors will be unstructured. If the unstructured covariance matrix results in a lack of convergence, the heterogeneous Toeplitz covariance structure, followed by the heterogeneous autoregressive covariance structure, followed by the compound symmetry, will be used. This order is specified according to a decreasing number of covariance parameters in the structure. The Kenward-Roger method will be used to estimate the denominator degrees of freedom. Type III tests for the least-squares (LS) means will be used for the statistical comparison; the 95% CI will also be reported. Treatment group comparisons with placebo at Week 16 (Visit 8) and all other visits will be tested.

When the ANCOVA is used, the model will include treatment, baseline CRP status, TNF inhibitor experienced or naïve, and baseline value. Type III sums of squares for the LS means will be used for the statistical comparison; the 95% CI will also be reported.

For variables that are not collected at each postbaseline visit, data may exist at visits where the variable was not scheduled to be collected, due to early discontinuation visits. In these situations, data from the early discontinuation visit that do not correspond to the planned collection schedule will be excluded from the MMRM analyses. However, the data will still be used in other analyses, including shift analyses, modified baseline observation carried forward (mBOCF) endpoint analyses and other categorical analyses.

Fisher's exact test will be used for all AE, baseline, discontinuation, and other categorical safety data. Continuous vital sign and laboratory values will be analyzed by an ANCOVA with treatment and baseline value in the model.

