10.3.7.4. Other Secondary Efficacy Analyses

There will be no adjustment for multiple comparisons. Analyses will be conducted for the other secondary efficacy objectives defined in Section 4. Specific details of analyses will be specified in the SAP.

Period 2 (Blinded Treatment Dosing Period)

Unless otherwise specified, the other secondary analyses during Period 2 will be based on the ITT Population.

Treatment comparisons in the proportion of patients achieving a categorical response at specified time points will be analyzed using the logistic regression model defined in Section 10.3.1.

Missing data will be imputed using the NRI method described in Section 10.3.4.

For all continuous efficacy variables that are collected at repeated visits, treatment group comparisons will be analyzed using the MMRM model defined in Section 10.3.1. No imputation

methods are applied to MMRM analysis. Additional analyses will be conducted using the ANCOVA model defined in Section 10.3.1; missing data will be imputed by the mBOCF method as described in Section 10.3.4. For continuous efficacy variables that are collected only once within Period 2, analyses will be made using the ANCOVA model with the mBOCF method.

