When the MMRM is used, the model will include treatment, baseline CRP status, TNF inhibitors experience, baseline value, baseline value-by-visit, visit, and treatment-by-visit interaction as fixed factors (except for the analysis of CRP, see paragraph below). The covariance structure to model the within-patient errors will be unstructured. If the unstructured covariance matrix results in a lack of convergence, the heterogeneous Toeplitz covariance structure, followed by the heterogeneous autoregressive covariance structure, followed by the compound symmetry, will be used. This order is specified according to a decreasing number of covariance parameters in the structure. The Kenward-Roger method will be used to estimate the denominator degrees of freedom. The restricted maximum likelihood (REML) will be used. Type III tests for the least-squares (LS) means will be used for the statistical comparison; the 95% CI will also be reported. Treatment group comparison with placebo at Week 16 (Visit 8) and all other visits will be reported.

For the analysis of CRP, the MMRM model will include treatment, baseline CRP status, TNF inhibitors experience, visit, and treatment-by-visit interaction as fixed factors.

When the ANCOVA is used, the model will include treatment, baseline CRP status, TNF inhibitors experience, and baseline value. Type III sums of squares for the LS means will be used for the statistical comparison; the 95% CI will also be reported.

For variables that are not collected at each postbaseline visit, data may exist at visits where the variable was not scheduled to be collected, due to early discontinuation visits. In these situations, data from the early discontinuation visit that do not correspond to the planned collection schedule will be excluded from the MMRM analyses (Andersen and Millen 2013). However, the data will still be used in other analyses, including shift analyses, or modified baseline observation carried forward (mBOCF) endpoint analyses, and other categorical analyses.

For selective efficacy measures, percent improvement will be calculated as $100 \times (\text{baseline score} - \text{observed scores}) / \text{baseline score}$, unless specified otherwise. If a patient has experienced an improvement, this measure will be positive. If a patient has experienced a worsening, this measure will be negative.

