6.3.2. Modified Baseline Observation Carried Forward

An mBOCF analysis will be performed on continuous efficacy and health outcome variables in the major and other secondary objectives. For patients discontinuing study drug due to an AE, the baseline observation will be carried forward to the corresponding time point for evaluation. For patients discontinuing study drug for any other reason, the last nonmissing observation before discontinuation will be carried forward to the corresponding time point for evaluation. Randomized patients without at least 1 postbaseline observation will not be included for evaluation with the exception of patients discontinuing study treatment because of an AE.

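### The SAP drops the continuous baseline value from the CRP MMRM without giving a reason, and its analysis table lists no baseline-adjusted Period 2 comparison for CRP

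*SAP*

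**What the plan says.** **Protocol.** The MMRM in 10.3.1 has treatment, baseline CRP status, TNF inhibitor experience, "baseline value, baseline value-by-visit, visit, and treatment-by-visit interaction as fixed factors". Section 10.3.7.4 gives it a wide scope: "For all continuous efficacy variables that are collected at repeated visits, treatment group comparisons will be analyzed using the MMRM model". CRP is drawn at every Period 2 visit, and change in CRP is a named other secondary endpoint. The same section adds a supporting analysis, with missing data imputed by modified baseline observation carried forward (mBOCF): "Additional analyses will be conducted using the ANCOVA model defined in Section 10.3.1". It also says "Specific details of analyses will be specified in the SAP". Section 10.3 allows a change that is not a principal feature without an amendment, provided that "the justification for making the change, will be described in the clinical study report".

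**SAP.** Section 6.1.1 repeats the protocol's MMRM but inserts "except for the analysis of CRP, see paragraph below", and then gives the reduced CRP model: "For the analysis of CRP, the MMRM model will include treatment, baseline CRP status, TNF inhibitors experience, visit, and treatment-by-visit interaction as fixed factors". CRP status means above, or not above, 5.00 mg/L. The SAP's ANCOVA includes the baseline value and makes no exception for CRP, but 6.1.1 restricts secondary ANCOVA to a selection of variables. Section 6.3.2 is broader: "An mBOCF analysis will be performed on continuous efficacy and health outcome variables in the major and other secondary objectives". In Table RHCH.6.4 the CRP row has the MMRM for four Period 2 populations and descriptive statistics for Period 3, and nothing else. Table RHCH.6.3 states no transformation of CRP.

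**The concern.** The two-level status factor leaves all variation in baseline CRP within each level unadjusted. Change from baseline contains the baseline value with a minus sign, so that variation goes straight into the residual. CRP is typically skewed, and the elevated stratum has no upper bound, so the leftover variation may be large. The baseline value is already collected and the protocol's model would use it. At stake are wider intervals and lower power for one anti-inflammatory endpoint. It is also unclear whether any baseline-adjusted CRP comparison is planned.

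**Working it through.** **1. The plan's own figure.** The plan gives no power or precision figure for CRP. Its only sample-size figure is 61 bDMARD-naïve patients per arm for ASAS40 (44% vs 16%, two-sided Fisher's exact test at 0.05). Exact enumeration gives 90.5% power at 61 and 89.9% at 60, so that figure stands. It does not depend on the CRP model.

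**2. Is the missing ANCOVA peculiar to CRP?** Continuous variable rows compared with placebo in Period 2:
- Table RHCH.6.4 has 11: ASDAS, BASDAI, BASFI, SPARCC spine, SPARCC SIJ, SSS, Patient Global, Spinal Pain, CRP, mobility, MASES.
- Table RHCH.6.6 has 6: SF-36 PCS, SF-36 MCS and domains, ASAS-HI, FACIT, WPAI, EQ-5D index and VAS.
- Of these 11 + 6 = 17, eight have MMRM only: Patient Global, Spinal Pain, CRP, mobility, MASES, SF-36 MCS and domains, ASAS-HI, FACIT.

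So the missing ANCOVA is not peculiar to CRP. But the other seven have their baseline value in the MMRM, and CRP does not.

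**3. Inputs for the size.** From the documents: 140 patients, 1:1, cut at 5.00 mg/L, about 60% elevated (84 elevated, 56 not). Assumed, because the documents are silent: lognormal CRP, log-SD 0.8 to 1.2, log-scale correlation ρ between baseline and Week 16 of 0.3 to 0.9, and no effect, a 30% fall or a halving on drug. The middle scenario is log-SD 1.0, ρ = 0.5.

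**4. mg/L scale, Week 16.** Change was regressed on treatment and status, with and without baseline CRP, in 10,000 simulated trials per scenario. The table shows the median ratio of CI widths (without / with baseline) for log-SD 0.8 / 1.0 / 1.2.

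| ρ | No effect | 30% fall | Halving |
|---|---|---|---|
| 0.3 | 1.21 / 1.24 / 1.26 | 1.29 / 1.33 / 1.37 | 1.36 / 1.40 / 1.44 |
| 0.5 | 1.15 / 1.18 / 1.20 | 1.23 / 1.27 / 1.30 | 1.31 / 1.34 / 1.39 |
| 0.7 | 1.09 / 1.12 / 1.13 | 1.17 / 1.20 / 1.23 | 1.25 / 1.29 / 1.32 |
| 0.9 | 1.03 / 1.05 / 1.06 | 1.13 / 1.15 / 1.16 | 1.22 / 1.24 / 1.28 |

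In the middle scenario:
- Estimated variance ratios are 1.39, 1.60 and 1.80; their square roots are 1.18, 1.26 and 1.34.
- Power without vs with baseline is 0.29 vs 0.45 (30% fall) and 0.69 vs 0.93 (halving).
- Type I error is 0.046 without and 0.045 with baseline.

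**5. Do the repeated visits recover the loss?** No. A six-visit MMRM (Weeks 1, 2, 4, 8, 12, 16; unstructured covariance; complete data; 18 of 140 assumed TNF-experienced; 1,000 trials per scenario) gives Week 16 width ratios of 1.19, 1.26 and 1.34 in the middle scenario and 1.03 at the mildest corner. Type I error is 0.047 without and 0.051 with baseline.

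**6. Log scale, closed form.** Let k be the share of log-CRP variance left within status: k = 1 − φ(0.2533)²/(0.6 × 0.4) = 1 − 0.1493/0.24 = 0.378. The variance ratio (without / with) is 1 + k(1 − ρ)/(1 + ρ).
- ρ = 0.3: 1 + 0.378 × 0.7/1.3 = 1.20, width ratio √1.20 = 1.10.
- ρ = 0.9: 1 + 0.378 × 0.1/1.9 = 1.02, width ratio √1.02 = 1.01.

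Estimating one more coefficient takes a little of this back, so about 0% to 10% extra width is a fair statement.

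**7. The cost of adjusting in mg/L.** If the effect is proportional, the slope of change on baseline differs between arms, and a common-slope model is misspecified. For halving:
- Middle scenario: mean estimate −5.23 with baseline vs −5.29 without (0.06/5.29 = 1%). The true difference is −0.5 × 5 × exp(0.2533 + 0.5) = −5.31.
- Log-SD 1.2, ρ = 0.9: −6.63 vs −6.96 (0.33/6.96 = 5%).
- Model-based 95% coverage, with vs without baseline: 0.933 vs 0.947 in the middle scenario, 0.895 vs 0.937 at log-SD 1.2, ρ = 0.9.

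With no effect, coverage is nominal for both models. Root mean squared error was lower with baseline in all 18 scenarios checked, so a net gain remains. On the log scale, coverage was nominal in every scenario simulated.

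**The case against.** The strongest reply is that this is a deliberate, permitted choice. The exception is flagged and the CRP model written out; SAP 6.2 states the baseline rule only as a general one; the protocol leaves details to the SAP and lets the justification wait for the study report. All of that stands, so a reader who inferred a protocol violation would go too far.

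Second, CRP differs from the other outcomes because the stratification factor is a cut of its own baseline, so dropping the continuous value may look like avoiding duplication. That makes the choice understandable. It does not make it efficient: the two terms can sit in one model, and the cut discards the within-level information.

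Third, a reader might infer that no baseline-adjusted CRP analysis exists anywhere in the plan. The documents do not support that. Protocol 10.3.7.4 and SAP 6.3.2 both point to an ANCOVA with mBOCF that would cover CRP. The restriction to selected variables and the silent CRP row make this unclear, not absent.

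Fourth, restoring the baseline value is not free. The undercoverage in step 7 means that, under a large proportional effect in mg/L, part of the narrower interval is not real precision. This objection stands and qualifies the larger entries in the table.

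Finally, every size here is assumed, and at the mildest corner about 21% of simulated trials gave a narrower interval without baseline. That also stands.

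**Conclusion.** The point holds as a minor one. For CRP alone, the SAP removes the protocol's continuous baseline adjustment without a stated reason, and its analysis table does not replace it. The expected cost is precision. In mg/L under the assumptions above, the 95% interval is 3% to 26% wider with no effect. It is nominally 13% to 37% wider for a 30% fall and 22% to 44% wider for a halving, with part of the difference under a large proportional effect due to undercoverage of the adjusted interval. On the log scale the cost is about 0% to 10%.

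A reader might infer that the omission biases the CRP comparison or inflates false positives. It does neither: randomisation keeps the status-only estimate unbiased on average, and simulated type I error is near 0.05 either way. CRP change is outside the multiplicity procedure, and the primary test, the major secondary tests and the sample size are untouched. Confidence in the text is high. Confidence in the size is limited by the absence of any CRP variance, correlation or effect in the documents.

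**What to change.** Before unblinding, do one of the following.

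1. Delete the CRP exception in SAP 6.1.1, so that CRP uses the protocol's MMRM: baseline CRP and baseline CRP-by-visit, together with CRP status and TNF inhibitor experience.
2. Keep the exception, state the reason, and add a baseline-adjusted ANCOVA with mBOCF for CRP to Table RHCH.6.4. This resolves the ambiguity for CRP only. The seven other MMRM-only rows would still leave open whether the tables or SAP 6.3.2 govern.

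The cost is a short SAP edit and no new data. Either baseline-adjusted analysis in mg/L carries the downside in step 7: a shift toward zero of up to about 5%, and coverage of about 0.93 in the middle scenario and 0.90 at the worst corner if CRP halves. A log-scale analysis is an optional safeguard, but it changes the estimand from a difference in mg/L to a ratio, which the SAP would need to say.
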